2. REVISION HISTORY AND RELEVANT DOCUMENTS

Below is a list of revision summaries of this statistical analysis plan.

Version	Date	Document Owner	Revision Summary
1.0	April 18, 2018	[REDACTED]	Initial version.
2.0	July 13, 2018	[REDACTED]	
Specified analysis methods for safety analyses in greater detail
 
Added summary of change from baseline in ACR summarized by baseline ACR category (ACR \leq300, ACR > 300)
 
Added analysis of covariance calculation of historical change in eGFR
 
Added analysis of covariance calculation of change in eGFR while in PHOENIX
 
Added comparison of eGFR before and after participation in PHOENIX
 
Changed the definition of baseline ACR

The analysis plan is based on the information from the following document:

Protocol Version 1.0, 17 August 2017

3. PURPOSE OF THE ANALYSIS PLAN

The purpose of this statistical analysis plan (SAP) is to pre-specify statistical analysis methods for supporting the completion of the clinical study report (CSR) of study 402-C-1702 for the investigational product bardoxolone methyl (BARD). This SAP will be used to analyze the safety, tolerability, and efficacy data collected during the study for four specified types of rare chronic kidney disease (CKD) collected during the study. This SAP complies with the International Conference on Harmonisation (ICH) guidance and relevant Food and Drug Administration (FDA) guidance documents. The analyses described in this plan have been prospectively defined prior to clinical database lock. The planned analyses identified herein may be included in regulatory submissions and/or future manuscripts. Endpoints will be assessed for each rare CKD cohort separately after the data have been locked.

This plan may be amended for reasons such as, but not limited to, protocol amendments, interim analysis results, and internal data reviews that take place prior to clinical database lock of the study. Exploratory analyses, which are not defined in this SAP, may be performed to support the clinical development program. Any post-hoc or unplanned analyses, which are performed for the CSR, but not defined in this SAP, will be clearly identified and documented in the CSR, as will any changes from the planned analyses as stated in the study protocol.

4. STUDY OBJECTIVES AND ENDPOINTS

4.1. Objectives

For patients within each rare CKD cohort enrolled in this study, the objectives are as follows:

4.1.1. Primary Objective

- To assess the change from baseline in estimated glomerular filtration rate (eGFR) in bardoxolone methyl-treated patients after 12 weeks of treatment.
- To assess the safety of bardoxolone methyl after 12 weeks of treatment.

4.2. Endpoints

4.2.1. Primary Efficacy Endpoint

- Change from baseline in eGFR at Week 12.

4.2.3. Safety Endpoints

Frequency, intensity, and relationship to study drug of AEs and SAEs, and change from baseline in the following assessments: vital sign measurements, 12-lead ECGs, clinical laboratory measurements, and weight.

5. STUDY DESIGN

[figure not shown]
5.1. Overall Study Design

This multi-center, open-label Phase 2 trial will study the safety, tolerability, and efficacy of bardoxolone methyl in qualified patients with the following rare chronic kidney diseases: CKD associated with type 1 diabetes (T1D), IgA nephropathy (IgAN), focal segmental glomerulosclerosis (FSGS), and autosomal dominant polycystic kidney disease (ADPKD). Patients will be enrolled in disease specific cohorts within the trial, and effectiveness of bardoxolone methyl in treating CKD will be assessed separately by cohort for each rare CKD. The trial will be open-label and enroll approximately 25 patients in each cohort of rare CKD etiology.

5.2. Randomization and Dosing

Randomization refers to patients receiving open-label bardoxolone methyl (BARD). All patients will receive BARD throughout the study as described in the protocol with the maximum bardoxolone methyl dose determined by urine albumin-to-creatinine ratio (ACR) at Screen B. The diagram below shows dose titration and maintenance schedules according to the baseline urine albumin-to-creatinine ratio (ACR) ≤ 300 mg/g or >300 mg/g. Patients with macroalbuminuria (300 mg/g $< \text{ACR} \leq 2500$ mg/g) at the Screen B visit will account for up to approximately 50% of patients enrolled within each cohort. Patients with ACR ≤ 300 mg/g at Screen B will be titrated to a maximum dose of 20 mg BARD, and patients with ACR > 300 mg/g at Screen B will be titrated to a maximum dose of 30 mg BARD. Patients will start with once-daily dosing at 5 mg and will dose-escalate to 10 mg at Week 2, to 20 mg at Week 4, and then to 30 mg at Week 6 (only if Screen B ACR >300 mg/g) unless contraindicated clinically and approved by the medical monitor.

Schema for Study of Bardoxolone Methyl in Patients with Rare Chronic Kidney Diseases

5.3. Assessments

All patients in the study will follow the same visit and assessment schedule. Table 2 lists the overall schedule of assessments for the study. Following randomization on Day 1, patients will be scheduled for assessments during treatment at Weeks 1, 2, 4, 6, 8, and 12, and by telephone contact on Days 3, 10, 21, 31, 38, and 45. Patients will also be scheduled for an in person follow-up visit at Week 16, four weeks after the end of treatment.

Table 2: Schedule of Assessments

Assessment	Screen A ^a	Screen B ^b	Day 1 ^c	Wk 1 (Phone) Day 3±2	Wk 1 Day 7±3	Wk 2 (Phone) Day 10±2	Wk 2 Day 14±3	Wk 3 (Phone) Day 21±2	Wk 4 Day 28±3	Wk 4 (Phone) Day 31±2	Wk 5 (Phone) Day 38±2	Wk 6 Day 42±3	Wk 7 (Phone) Day 45±2	Wk 8 Day 56±3	Wk 12 or EoT ^d Day 84±3	Wk 16 or F/U Day 112±3
Informed consent	X															
Inclusion/ exclusion	X		X ^e													
Demographics and baseline disease characteristics	X															
Concomitant medications	X	X	X	X	X	X	X	X	X	X	X	X	X	X	X	X
Medical history	X															
Height	X															
Weight in clinic/BMI	X		X		X		X		X			X		X	X	X
Weight at home			X	X	X	X	X	X	X	X	X	X	X	X	X	
Dispense weight diary			X				X		X			X		X		
Collect/review weight diary				X	X	X	X	X	X	X	X	X	X	X	X	
ECG	X														X	X
Echocardiogram ^f	X															
Vital sign measurements	X		X		X		X		X			X		X	X	X
Physical exam	X		X		X		X		X			X		X	X	X
Pregnancy test for WOCBP ^g	X	X	X						X					X	X	X
Study drug administration				-----X-----												
Dispense study drug			X				X		X			X		X		
Collect study drug							X		X			X		X	X	
Telephone contact				X		X		X		X	X		X			
Adverse event collection			x ^h	X	X	X	X	X	X	X	X	X	X	X	X	X
Kidney biopsy ⁱ	X															
Fasting C-peptide level ^j	X															

Genetic testing ^k	X															
Assessment	Screen A ^a	Screen B ^b	Day 1 ^c	Wk 1 (Phone) Day 3±2	Wk 1 Day 7±3	Wk 2 (Phone) Day 10±2	Wk 2 Day 14±3	Wk 3 (Phone) Day 21±2	Wk 4 Day 28±3	Wk 4 (Phone) Day 31±2	Wk 5 (Phone) Day 38±2	Wk 6 Day 42±3	Wk 7 (Phone) Day 45±2	Wk 8 Day 56±3	Wk 12 or EoT ^d Day 84±3	Wk 16 or F/U Day 112±3
Clinical chemistry (incl. eGFR)	X	X	X		X		X		X			X		X	X	X
BNP and NT-proBNP	X		X		X		X		X			X		X	X	X
IGF-1 and serum ketones	X		X		X		X		X			X		X	X	X
Hematology	X		X				X		X			X		X	X	X
Urinalysis and microscopy	X		X				X		X			X		X	X	X
Urine collection for ACR ^e		X	X						X					X	X	X
██████████															X	X
██████████															X	X
Virus serology	X															
PK samples ^f															X	

^a Total Screening period should not exceed 6 months.

^b Screen B visit should be no more than 30 days prior to Day 1.

^c Day 1 is the day of administration of the first dose. **On Day 1, all procedures should be performed before study drug administration.**

^d Patients who terminate from the study prior to the Week 12 study visit should be brought back to the clinic as soon as possible for early termination assessments (*i.e.*, end-of-treatment visit) as well as a follow-up visit 4 weeks later.

^e Screening eligibility procedures do not need to be repeated on Day 1; however, a review of any changes in eligibility criteria should be evaluated prior to Day 1 procedures, and a urine pregnancy test should be performed for WOCBP.

^f An echocardiogram performed at the Screen A visit or within 6 months prior to Day 1 may be used to determine eligibility.

^g A serum pregnancy test will be performed at the Screen A visit for WOCBP or at any point in time if a pregnancy is suspected. All other pregnancy assessments will be urine pregnancy tests.

^h AE assessments on Day 1 should be performed following study drug administration.

ⁱ Only patients enrolling in the IgA nephropathy cohort or the FSGS cohort are required to have a kidney biopsy. Patients with definitive diagnosis of IgA nephropathy or FSGS from previous biopsy will not have a kidney biopsy as part of the study, but must provide diagnosis documentation from previous kidney biopsy for eligibility.

^j Only patients enrolling in the T1D cohort are required to have fasting C-peptide levels assessed. Patients should be instructed to fast prior to study visit.

^k Only patients enrolling in the ADPKD disease cohort are required to have genetic testing. Patients with confirmed PKD1 mutations from previous genetic testing will not have genetic testing performed as part of the study, but must provide documentation of genetic mutation for eligibility.

^l Albumin to creatinine ratio will be measured by first morning void spot urine collection. Appropriate containers for the collection will be provided to the patient at the visit prior to collection.

^m Patients must be instructed to not take their study drug prior to coming to the clinic for visits when PK samples will be collected. Patients must administer the study drug dose in the clinic on PK sample collection visits after the 0 hour PK blood sample is collected. Patients will have blood samples for PK analysis drawn just prior to (0 hour) and after (2 and 4 hours) dose administration.

Abbreviations: EoT= end-of-treatment; ECG = electrocardiogram, F/U = follow-up; PK = pharmacokinetic, WOCBP = women of child-bearing potential

5.3.1. Efficacy Measurement and Variable

Central laboratory reported eGFR values will be used to calculate change from baseline in eGFR, the primary efficacy endpoint for the study. Baseline eGFR value will be calculated as described in Section 7.2.1 below.

5.3.2. Safety Measurements and Variables

Safety will be assessed by repeated clinical evaluation, including AEs, SAEs, vital signs, physical examinations, 12-lead ECGs, clinical laboratory tests (i.e., chemistry, B-type natriuretic peptide [BNP], N-Terminal Pro-Brain Natriuretic Peptide [NT-Pro BNP], Insulin-Like Growth Factor-1 [IGF-1], serum ketones, hematology, ACR, spot urinalysis, and urine microscopy), body weight, visual acuity assessments, audiology assessments, and concomitant medications.

5.3.3. Pharmacokinetics Measurements and Variables

Pharmacokinetic (PK) samples will be collected on Day 84 \pm 3 days, prior to study drug dosing (pre-dose; 0 hour), and at post-dose hours 2 and 4. The PK variables include bardoxolone methyl plasma concentration-time data, and estimated PK parameters.

6. SAMPLE SIZE AND POWER

With 25 patients in each cohort, the study will have approximately 80% power to detect a change from baseline in eGFR relative to zero. [REDACTED]

- [REDACTED]
- [REDACTED]
- [REDACTED]
- [REDACTED]

[REDACTED] The primary efficacy endpoint will be analyzed separately for each rare chronic kidney disease cohort. [REDACTED]

7. GENERAL CONSIDERATIONS

The analysis sets, as defined in Section 8, will be used for efficacy, safety, tolerability, and PK analyses. Patient listings of all analysis data that support summary tables and/or figures will be provided along with relevant source data from the electronic case report forms (eCRFs). Measurements from patients excluded from the pre-defined analysis sets or extra measurements (such as unscheduled or repeat assessments) will not be included in summary tables unless

specified otherwise, but will be included in the patient listings. Missing data will not be imputed, unless otherwise specified. In general, a separate set of tables, listings, and figures will be generated for each cohort. Select tables may be generated as appropriate that summarize data for all cohorts pooled. Patient listings will be sorted by patient number first, then assessment date (time and parameter, as applicable).

Unless otherwise specified, descriptive statistics for continuous variables will include the number of patients with data (N), mean, standard deviation (SD), median, minimum, and maximum. The same number of decimal places as in the observed value will be presented when reporting minimum and maximum; 1 more decimal place than in the observed value will be presented when reporting mean and median; and 2 more decimal places than in the observed value will be presented when reporting SD.

Categorical/qualitative data will be presented using frequency counts and percentages. All percentages will be rounded to 1 decimal place, unless otherwise specified. Percentages equal to 100 will be presented as 100% and no percentages will be presented for zero frequencies. Where individual variable values are missing, categorical data will be summarized based on reduced denominators (i.e., only patients with available data will be included in the denominators). For summaries of AEs and concomitant medications (CM), the percentages will be based on the number of patients who received study drug.

Results of statistical analyses will be reported by rare CKD cohort using summary tables, listings, and figures (TLFs). The ICH numbering convention will be used for all TLFs. The following conventions will be followed:

- Unless otherwise noted, all statistical testing will be two-sided and will be performed at the 0.05 significance level.
- Tests will be declared statistically significant if the calculated p-value is <0.05 .

All analyses and summaries will be produced using SAS[®] version 9.3 (or higher).

7.1. Derived Variables

7.1.1. Age

Age (years) will be calculated as the number of years between date of birth and date of informed consent, expressed as an integer.

7.1.2. Study Day

Study Day will follow the CDISC SDTM standard and is defined as follows:

- assessment date – date of first study drug dosing + 1, where the assessment date is on or after the date of first study drug dosing;

- assessment date – date of first study drug dosing, where the assessment date is before the date of first study drug dosing.

7.1.3. Estimated Glomerular Filtration Rate

Estimated glomerular filtration rate (eGFR) value will be calculated at the central laboratory and used in data analyses. The equation used to calculate eGFR for each patient will be the Chronic Kidney Disease Epidemiology Collaboration (CKD-EPI) equation:

- $eGFR \text{ (mL/min/1.73 m}^2\text{)} = 141 \times \min(S_{cr}/\kappa, 1)^\alpha \times \max(S_{cr}/\kappa, 1)^{-1.209} \times 0.993^{\text{Age}} \times 1.018 \text{ [if female]} \times 1.159 \text{ [if black]}.$

Where S_{cr} is serum creatinine (mg/dL), κ is 0.7 for females or 0.9 for males, and α is -0.329 for females or -0.411 for males. Min indicates the minimum of S_{cr}/κ or 1, and max indicates the maximum of S_{cr}/κ or 1.

Historical serum creatinine and eGFR values will be treated separately from data collected as part of the trial's central lab assessments. Historical eGFR values will be calculated from historical serum creatinine results.

Missing eGFR values will not be imputed for the primary analysis of efficacy. The eGFR values collected after the window of the date of last dose for patients who do not complete study treatment will not be included in the analysis.

7.1.4. Urine Albumin and Urine Albumin to Creatinine Ratio

Urine albumin to creatinine ratio (ACR) will be calculated at the central laboratory using the formula below:

- $ACR = \text{Urine Albumin (mg/dL)} / \text{Urine Creatinine (g/dL)}$

Urine creatinine may need to be converted from mg/dL to g/dL. The central laboratory uses an assay that has a lower limit of detection (LLD) and an upper limit of detection (ULD) for urine albumin. Urine albumin results below LLD will be imputed with LLD/2 in mg/dL. Urine albumin results above ULD will be imputed with the ULD value. Where imputation is necessary, the imputed urine albumin results will be used along with the urine creatinine result provided by the central laboratory for calculating ACR.

7.1.5. Electrocardiogram Fridericia Corrected QT Interval

Electrocardiogram intervals, including the Fridericia corrected QT interval (QTcF), will be assessed locally at each site. In the event that QTcF interval is not provided, it will be calculated from QT and RR intervals using the following formula:

- $QTcF = QT / \sqrt[3]{RR}$

Where $RR = 60 / (\text{Heart Rate})$.

7.2. Baseline Values

Baseline values are defined as the last non-missing assessment prior to the first study drug dosing, unless otherwise specified below.

7.2.1. Estimated Glomerular Filtration Rate

The Screening eGFR value is the average of the last two eGFR measurements collected prior to Day 1, for example $(\text{Screen A eGFR} + \text{Screen B eGFR}) / 2$. Unscheduled eGFR values collected prior to Day 1 will be used in the calculation of Screening eGFR if the unscheduled eGFR values are within the last two eGFR measurements collected prior to Day 1. Baseline eGFR will be calculated as a weighted average of the Day 1 measurement and the Screening measurement as shown below:

- $\text{Baseline eGFR} = 0.5 \times \text{Day 1 eGFR} + 0.5 \times \text{Screening eGFR}$

However, if no Day 1 eGFR value exists or Day 1 study drug administration occurred before Day 1 lab collection, then Baseline eGFR will equal Screening eGFR.

7.2.2. Serum Creatinine

The Screening SCr value is the average of the last two SCr measurements collected prior to Day 1, for example $(\text{Screen A eGFR} + \text{Screen B eGFR}) / 2$. Unscheduled SCr values collected prior to Day 1 will be used in the calculation of Screening SCr if the unscheduled SCr values are within the last two SCr measurements collected prior to Day 1. Baseline SCr will be calculated as a weighted average of the Day 1 measurement and the Screening measurement as shown below:

- $\text{Baseline SCr} = 0.5 \times \text{Day 1 SCr} + 0.5 \times \text{Screening SCr}$

However, if no Day 1 SCr value exists or Day 1 study drug administration occurred before Day 1 lab collection, then Baseline SCr will equal Screening SCr.

7.2.3. Vital Sign Assessments

Baseline vital sign assessments are defined as the average value of measurements (from scheduled and unscheduled visits) collected up through Day 1, prior to first dose of study drug.

7.2.4. Albumin/Creatinine Ratio (ACR)

Baseline ACR is defined as the average of Screen B and Day 1 ACR values.

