### 12.2.2. Efficacy Variables

Change from baseline in eGFR will be used to determine the primary efficacy endpoints. Baseline ACR and eGFR values will be calculated using averages of measurements collected up through Day 1, prior to first dose of study drug. The SAP will provide details of these calculations.

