7.3. Analysis Windows

Because clinical visits may occur outside protocol specified windows, instead of relying solely on visit labels in the clinical database, analysis visits and their windows are defined using Study Day (See Section 7.1.2). Analysis visit windows are presented in Table 3 by type of assessments and/or measurements.

If more than one on-treatment assessments and/or measurements exists for a parameter within a visit window, the one that is closest to the protocol scheduled time point (or target Study Day) will be used for analysis and summary. If more than one off-treatment assessment exists, the one closest to the target study day will be used for analysis and summary.

Table 3: Analysis Windows

Visit Scheduled Time Point	Target Study Day	Analysis Visit Windows	
		All Other Assessments	12-lead ECG
Screen A	-60	-180 to -2	-180 to 1
Screen B ^a	-1	-30 to -1	-
Day 1	1	1	-
Week 1	7	2 to 10	-
Week 2	14	11 to 21	-
Week 4	28	22 to 35	-
Week 6	42	36 to 49	-
Week 8	56	50 to 70	-
Week 12	84	71 to 98	2 to 98
Week 16	112	> 98	-

^aScreen B is after Screen A, and no more than 30 days prior to Day 1

Note: Study Day is relative to the first date of study drug administration (Study Day 1). Visit Scheduled Time Point = Analysis Visit (AVISIT), after applying the analysis windows described above. The Week 16 visit has the additional restriction that assessments must be collected after last dose of study treatment. For patients who terminated treatment prior to Week 12, use Week 16 as follow-up visit.

If more than one measurement is collected equidistant to the target Study Day and on different collection date/time, the first measurement will be flagged for analysis and summary. If more than one measurement is closest to the target Study Day and collected on the same date, the average of those measurements will be used for analysis and summary.

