11.1.2. Statistical Model

The MMRM model will include the change from baseline in eGFR value as the dependent variable, protocol scheduled time point (analysis visit) as a fixed effect, patient as a random effect, and the baseline eGFR and log-transformed baseline ACR as continuous covariates. Within-patient correlations will be modeled using an unstructured covariance structure. Time ordering is a repeated measure within patients. It is assumed that errors for different patients are independent with an unstructured covariance structure. The estimation method for the model will be restricted maximum likelihood (REML). The SAS pseudo-code is as follows:

```
proc mixed data=efficacy method=reml;  
  class usubjid avisitn;  
  model chg=avisitn base_egfr lbase_acr;  
  repeated avisitn / subject=usubjid type=un rcorr;  
  lsmeans avisitn / diff cl alpha=0.05;  
run;
```

In the event the MMRM model with an unstructured covariance structure does not converge, the following covariance structures will be as substitution in the following order. Each subsequent covariance structure will be used only if all previous covariance structure(s) is (are) used and the model(s) did not converge.

1. Toeplitz covariance structure (assuming measurements from samples taken closer together in time are more highly correlated than those from samples taken farther apart).
2. First order of auto-regressive [AR(1)] covariance structure (assuming measurements from samples taken closer together in time are more highly correlated than those from samples taken farther apart).
3. Compound symmetry covariance structure (assuming equal correlation for measurements from a patient, regardless of how far apart in time when they were taken).

A separate MMRM model will be analyzed for each rare CKD cohort.

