12.7.3. Change from Baseline in ACR

Within each rare CKD cohort, the change from baseline ACR will be summarized for all patients, as well as by baseline ACR category ($ACR \leq 300$, $ACR > 300$). Summaries of ACR will use the geometric mean with 95% confidence intervals instead of the arithmetic mean, and will display ACR results in units of mg/g. Changes from baseline in ACR will be reported as the post-baseline/baseline ratios and will be summarized by geometric means with 95% confidence intervals at each time point.

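### Baseline ACR, read as an arithmetic average under a geometric post-baseline/baseline ratio, pulls the ACR ratio modestly but systematically downward

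*SAP*

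**What the plan says.** SAP 7.2.4 gives the baseline in one sentence: "Baseline ACR is defined as the average of Screen B and Day 1 ACR values". No formula follows and no scale is named. Protocol 12.2.2 is no more specific ("Baseline ACR and eGFR values will be calculated using averages of measurements collected up through Day 1") and leaves the details to the SAP.

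Two things in the SAP indicate what is meant. In 7.2.1 the Screening eGFR is also an average ("The Screening eGFR value is the average of the last two eGFR measurements collected prior to Day 1"), and the worked example there adds two values and divides by two; 7.2.2 does the same for serum creatinine. Where the SAP wants a geometric mean it says so, as in 12.7.3: "Summaries of ACR will use the geometric mean with 95% confidence intervals instead of the arithmetic mean".

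The change measure is set out in 12.2 and again in 12.7.3: "Changes from baseline in ACR will be reported as the post-baseline/baseline ratios and will be summarized by geometric means with 95% confidence intervals". The numerator is normally a single value, because under 7.3, when a window holds several on-treatment results, "the one that is closest to the protocol scheduled time point (or target Study Day) will be used for analysis and summary". Only ties collected on the same date are averaged.

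The same baseline ACR enters the baseline of ln(ACR)/eGFR (7.2.5, analysed in 12.7.2). It also appears in the primary eGFR model (11.1.2), but only as a covariate.

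**The concern.** The denominator is averaged on the raw scale and the ratio is then analysed on the log scale. For a skewed, noisy measurement these do not match: a raw average of two values sits above their geometric mean, while the single post-baseline value has no matching uplift. A cohort whose albuminuria did not change would be expected to show a geometric mean ratio below 1.

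The direction matters because rising urinary albumin is a recognised effect of this drug (Protocol 5.1.2.6), has its own monitoring guidance (Protocol 9.1.6), and ACR change by baseline category is one of the additional safety endpoints in SAP 12.7. The mismatch moves that summary in the reassuring direction. Every patient receives active drug, so each ratio is read against 1 and no control group carries the same shift.

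**Working it through.** **Inputs.** From the documents: two baseline values per patient (SAP 7.2.4), normally one post-baseline value per window (7.3), the ratio summarised by geometric mean with a 95% CI (12.2, 12.7.3), and 25 patients per cohort (SAP 6). Not in the documents, so assumed: within-patient errors normal on the log scale with SD s from 0.20 to 0.60, and correlation r between the Screen B and Day 1 errors of 0 or 0.5. The plan states no figure for ACR change, so there is none to reproduce.

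**Step 1: one patient.** Let d = ln(ACR at Screen B) − ln(ACR at Day 1). Then

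ln(arithmetic mean) − ln(geometric mean) = ln cosh(d/2) ≥ 0.

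The gap is zero only when the two values are equal. Example: 200 and 400 mg/g give an arithmetic mean of 300 and a geometric mean of √(200 × 400) = 282.8. Since 282.8/300 = 0.943, that patient's ratio is 5.7% lower with the arithmetic baseline.

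**Step 2: expected shift with no true change.** d is normal with mean 0 and variance 2s²(1 − r). The expected log shift is E[ln cosh(d/2)], roughly s²(1 − r)/4. By numerical integration, with the expected ratio equal to exp(−shift):

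| s (assumed) | log shift, r = 0 | ratio, r = 0 | ratio, r = 0.5 | true +20% reads as (r = 0) |
|---|---|---|---|---|
| 0.20 | 0.0099 | 0.990 | 0.995 | +19% |
| 0.30 | 0.0220 | 0.978 | 0.989 | +17% |
| 0.45 | 0.0483 | 0.953 | 0.976 | +14% |
| 0.60 | 0.0833 | 0.920 | 0.958 | +10% |

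The last column is 1.20 × the ratio at r = 0. The downward shift is therefore about 1% to 8% with independent errors and about half that at r = 0.5.

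**Step 3: consequence at n = 25.** Simulation of 40,000 cohorts, all errors independent, t-based 95% CI on the log ratios:

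| s | No change: CI wholly below 1, arithmetic baseline (nominal 2.5%) | True +20%: CI wholly above 1, arithmetic vs geometric baseline |
|---|---|---|
| 0.30 | 4.9% | 55% vs 66% |
| 0.45 | about 6% | 21% vs 35% |
| 0.60 | about 7.5% | 10% vs 22% |

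Coverage with the arithmetic baseline is 93.8%, 92.6% and 90.8% at within-patient CV 0.3, 0.5 and 0.8 (s about 0.29, 0.47 and 0.70). With the geometric baseline the mean ratio returns to 1.00 and coverage to about 95%. For scale, the CI half-width is about 16% at CV 0.3 and 27% at CV 0.5, against shifts of about 2% and 5%.

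**Step 4: ln(ACR)/eGFR.** The baseline term is ln(baseline ACR)/baseline eGFR. An arithmetic baseline raises it by ln cosh(d/2)/baseline eGFR, so the change from baseline falls by that amount. At s = 0.45 and r = 0 the expected fall is 0.0483/30 = 0.0016 at a baseline eGFR of 30 and 0.0483/90 = 0.0005 at 90, the ends of the eligible screening range.

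**Step 5: primary model.** In 11.1.2 the outcome is change in eGFR, and baseline ACR enters only through "log-transformed baseline ACR as continuous covariates". It is not a denominator of the outcome, so this mechanism does not operate there.

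**The case against.** The strongest case against has five parts.

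- **The scale is unstated.** A reader might say the SAP specifies an arithmetic mean. It does not use that word, and a programmer who took the geometric mean would remove the problem. This stands as a limit on the wording. Even so, the examples in 7.2.1 and 7.2.2, and the explicit use of the geometric mean elsewhere, make arithmetic the reading most likely to be programmed. If a geometric mean was intended, the text still needs to say so.
- **The size is assumed.** Neither the within-patient SD nor the correlation between two visits no more than about 30 days apart is given. This stands. The direction of this component is certain; its size is not.
- **It is small beside the CI, and safety does not rest on it.** True. Observed ACR is also summarised, patients above 3500 mg/g are counted, individual rises are monitored under Protocol 9.1.6, and listings let anyone recompute the ratio. No decision rule hangs on 12.7.3. That limits the importance, but does not justify keeping a bias that one line removes.
- **ACR is not handled on the log scale throughout.** Correct. The categories at 300 and 1000 mg/g (9.3), the 300 mg/g split (12.7.3) and the 3500 mg/g threshold (12.2) are on the raw scale, and a raw average suits them.
- **Other selection effects exist.** The Screen B cap of 2500 mg/g may cause regression to the mean in the opposite direction. The net bias in the trial may therefore differ from this component, which is a reason not to claim a net figure.

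A reader might also infer that the primary eGFR result is compromised because 11.1.2 uses baseline ACR. The documents do not support that, for the reason in the last step of the working.

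**Conclusion.** The point holds for the ACR ratio summaries in SAP 12.2 and 12.7.3 and for the change in ln(ACR)/eGFR in 12.7.2. On the natural reading of 7.2.4, each patient's ratio is equal to or lower than it would be with a baseline on the matching scale, so rises are understated and falls overstated. The size is about 1% to 8% for an assumed log SD of 0.20 to 0.60 with independent errors, and roughly half that at an error correlation of 0.5. The direction rests only on arithmetic averaging and a single post-baseline value; the size rests on assumptions that the documents cannot settle.

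This is a correction worth making, but not one that overturns a safety conclusion. It does not bias the primary test, and the documents do not support reading it as concealing a large rise in albuminuria.

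**What to change.** In SAP 7.2.4, define baseline ACR for the ratio and ln(ACR)/eGFR analyses (7.2.5, 12.2 and 12.7) as the geometric mean of Screen B and Day 1: exp{[ln(Screen B ACR) + ln(Day 1 ACR)]/2}. State the rule for a patient with only one of the two values. No change to 11.1.2 is needed to remove a bias; using the same definition there would be for consistency only.

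The cost is one line of text and one derivation, and SAP section 3 allows amendment before database lock. There is a small downside. If the same baseline also sets the analysis categories in 9.3 and 12.7.3, a few patients near 300 or 1000 mg/g may move down a category, because the geometric mean is never higher. The SAP should say which baseline defines the categories. Dose assignment under SAP 5.2 uses Screen B ACR and is not touched by this derivation.

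The change does not remove regression to the mean within the baseline-category summaries of 12.7.3, so those still need a caution. If the sponsor prefers to keep the raw average, a sensitivity summary with the geometric baseline would show how much it matters.
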